3.1.1 Screening Procedures (Days -28 to -1)

Potential subjects will be screened during the 4 weeks preceding Day 0 to determine if they meet the inclusion and exclusion criteria, and if all criteria are satisfied, will be eligible to participate in the clinical trial. All general and indication-specific entry criteria must be met before study entry. Subjects who enter the trial will be provided with an Ethics Committee approved written informed consent for review and signature (See Appendix 3).

3.1.2 Clinic Admission (Day 0)

After enrollment and an initial assessment (time zero data), patients will be treated with DermGEN decellularized human dermal matrix. Following standard of care procedures, the wound will be debrided to provide healthy tissue margins and a bleeding wound bed. A 4 cm x 4 cm piece of DermGEN will be prepared by sizing to approximately 2-3 mm past the margins of the ulcer with the dermal side in contact with the wound bed, and securing it to the wound with sutures.

A non-adherent dressing will be used to cover the DermGEN graft, followed by a moisture retentive dressing and either (a) a compressive dressing; or (b) a vacuum-assisted wound closure dressing (“VAC-Assist”). All patients will have the same brands and types of dressings applied, except for the first 1 to 3 patients treated (see final paragraph, section 3.1 above).

3.1.3 Subsequent Clinic Visits (Weeks 1, 2, 3, 4, 12, and 20)

Follow up visits will be at 1, 2, 3, 4, and 12 and 20 weeks and as required for clinical care of active detriments to healing and local wound care.

The LUMT will be administered at each of the 1, 2, 3, 4, and 12 and 20 weeks FU visits in order to capture data relevant to the study. The SF-12 survey will be administered at time 0, 4, 12 and 20 weeks post-treatment.

Digital photography will be utilized to capture the appearance and size of the ulcer at each visit. Clinic photographs will be taken with the digital camera supplied by DeCell. Other photographs to demonstrate the condition of the wound between clinic visits may be taken with any digital camera (including smartphones), and a measuring ruler must be visible in each picture. Patients and caregivers are to be encouraged to take their own photographs if the wound ever becomes uncovered or visibly stained – again ensuring that some ruler appears in the photos – and copies should be provided to the study staff.

Dressing changes will occur at each visit, and a record of these changes kept. All patients will receive appropriate wound off-loading using a device appropriate to ulcer location. All post-treatment complications will be recorded on the appropriate case report form.

Patients with complications that may be managed by further treatment, for example antibiotic administration or reapplication of another DermGEN graft, will remain in the study.

For any subject who requests study withdrawal or is withdrawn by the investigator, the reason for study discontinuance will be recorded by the Principal Investigator on the appropriate case report form.

3.2 Dose Selection and Use

DermGEN will be applied on Day 0, following the directions for use.

If at a subsequent visit the product material is deteriorating, then the investigator may, at his discretion, remove the remaining product material, prepare the wound bed appropriately, and apply one new DermGEN treatment. In such cases, the remaining course of the study will continue unchanged, and the patient’s last visit will still be at Week 20.

The reasons for any second application of DermGEN must be carefully documented, together with before and after photographs showing the deteriorating specimen in situ before removal and also the new specimen in place prior to applying new dressings.

4. STUDY POPULATION

4.1 General Considerations

A total of 15-20 patients will be enrolled for the study, with patients enrolled in each of the following participating centers: Halifax and Toronto.

Ages will include 18 and older from both sexes. Potential subjects will be screened to determine if they meet the inclusion and exclusion criteria and if all entry criteria are achieved, will be eligible to participate in the clinical trial. All general and indication-specific entry criteria must be met before study entry. Subjects who enter the trial will be provided with an Ethics Committee approved written informed consent for review and signature.

4.2 Inclusion Criteria

A subject will be considered eligible to participate in this study if each of the following inclusion criteria is satisfied:

1. Patient with documented stable Type I or II diabetes ($HbA_{1c} > 7.0$ within 1 month prior to Day 0).
2. Patient's ulcer has been present for a minimum of 2 weeks as of Day 0.
3. Study ulcer has healed $< 30\%$ in size during the 2 weeks prior to Day 0.
4. Ulcer area is ≥ 1 cm² prior to debridement at Day 0 of study.
5. Ulcer extends through dermis and into subcutaneous tissue but without exposure of muscle, tendon, bone or joint capsule.
6. Ulcer is free of necrotic debris and clinical infection, and is comprised of healthy vascular tissue suitable for skin grafting on Day 0.
7. Patient has adequate circulation to the foot as evidenced by palpable pulse or pulse detectable with Doppler ultrasound, and lack of visible cyanosis in skin bordering the ulcer.
8. Female patients are not pregnant at time of, or during study.
9. Patient and caregiver ready and willing to participate and comply with follow-up regime.
10. Patient or legal representative has read and signed the Institutional Ethics Review Board approved informed consent form.

4.3 Exclusion Criteria

A subject will not be considered eligible to participate in this study if any one of the following exclusion criteria is satisfied:

1. Evidence of gangrene on affected foot.

2. Ulcer is over Charcot deformity (fractures or dislocation).
3. Ulcer is non-diabetic in etiology.
4. Ulcer has tunnels or sinus tracts that cannot be completely debrided.
5. Medical condition(s) that in the Investigator's opinion make the patient inappropriate for study
6. Patient has/had malignant disease not in remission for 5 years or more
7. Patient has acute or chronic hepatitis, cirrhosis, serum albumin <2.0 gm/dL, or has alkaline phosphatase or LDH at twice the normal upper limit
8. Patient receiving oral or parenteral corticosteroids, immunosuppression or cytotoxic agents, or is anticipated to require such agents during study
9. Patient received radiation therapy within 30 days of Day 0 of study
10. Patient has AIDS or is infected with HIV
11. Patient has participated in another study using investigational drug(s) or device within the previous 30 days
12. Obvious clinical signs and symptoms of ongoing cellulitis or osteomyelitis
13. Patient has any other condition which seriously compromises their ability to complete the study
14. Patient has known allergies to antibiotics, such as penicillin and streptomycin
15. Patient has a history of bleeding disorder
16. Patient received elective osseous procedures to the study foot within 30 days prior to screening visit, *except* that patients whose DFU overlies an area of treated osteomyelitis may be included, providing there exists a suitable base for application of the DermGEN.

4.4 Concomitant Medications

In general, there is no reason to expect medications to interact with DermGEN. Only medications considered prejudicial to wound healing are prohibited. These include, but are not necessarily restricted to, the following:

- Corticosteroids, either topical near the ulcer, or systemic
- Immunosuppressive drugs of any type, either topical near the ulcer, or systemic
- Anti-infective agents used topically, if believed to be cytotoxic

Patients will remain on all medications prescribed to treat their diabetes and associated conditions as determined at the point of enrolment. If there are any changes to a patient's medication (dosing, new medications, alternate medications) during the study, this will be noted in the patient's study file and reviewed by the study supervising clinician to determine continued eligibility of the patient in the study. Patients with complications that may be managed by further treatment, for example antibiotic administration or reapplication of another DermGEN graft, will remain in the study.

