4.6.2 Subject Withdrawal

Any subject who voluntarily withdraws (e.g., withdrawal of consent) or is discontinued (e.g., as a result of an AE) from the study prior to the completion of all assessments will be considered as having withdrawn from the study.

Subjects may be withdrawn from the study under any of the following circumstances:

- (i) patient is non-compliant with home care regime (e.g. not wearing off-loading cast),
- (ii) presence of recurrent, untreatable infection,
- (iii) patient develops illness after enrollment that may unduly affect ulcer healing,
- (iv) patient requires more than one re-treatment with DermGEN

When an event such as a family emergency, a transient intercurrent illness (such as a cold) unrelated to study medication, or a remediable act of non-compliance prevents a subject from participating in a scheduled visit but the subject wishes to continue in the study, then with the agreement of the investigator, the clinical staff may attempt to reschedule the visit and retain the subject in the study.

If a subject is prematurely discontinued from participation in the study for any reason after treatment has begun, the investigator or designee must make every effort to perform the assessments scheduled for the Follow-Up Visit (section 6.5.1). The reason for withdrawal will be recorded in the CRF and the subject's medical record.

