6.2.4 Medication History

All medications (prescription and non-prescription, herbal medications, or investigational drugs) taken by the subjects during the 14 days prior to Screening and during the remainder of the study will be recorded in the source documentation. The reported medications will be reviewed and evaluated by the investigator or designee to determine if they affect the subject's eligibility to participate in the study.

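### A medication change after grafting reopens eligibility, and a removed patient is owed only one best-effort visit, so Week 12 healing can go unknown

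*Protocol*

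**What the plan says.** Under sections 4.4 and 6.2.5, any dose change, new drug or substituted drug during the study is noted and then "reviewed by the study supervising clinician to determine continued eligibility of the patient in the study". Section 6.2.4 adds that drugs taken "during the 14 days prior to Screening and during the remainder of the study will be recorded in the source documentation" are to be "reviewed and evaluated by the investigator or designee to determine if they affect the subject's eligibility to participate in the study".

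Section 4.4 also sets a limit: "Only medications considered prejudicial to wound healing are prohibited". Its list is expressly not exhaustive. It covers corticosteroids and immunosuppressants, whether systemic or topical near the ulcer, and "Anti-infective agents used topically, if believed to be cytotoxic". Exclusion 8 in 4.3 is worded differently: "Patient receiving oral or parenteral corticosteroids, immunosuppression or cytotoxic agents, or is anticipated to require such agents during study". Section 4.4 keeps patients with manageable complications, such as those needing antibiotics or a regraft, in the study.

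Sections 4.6.2 and 6.1.3 give the same four withdrawal reasons: non-compliance with home care, recurrent untreatable infection, a new illness that may affect healing, and need for more than one re-treatment. A patient who leaves or is discontinued "prior to the completion of all assessments will be considered as having withdrawn from the study". After premature discontinuation for any reason, the investigator "must make every effort to perform the assessments scheduled for the Follow-Up Visit (section 6.5.1". Section 6 of the protocol ends at 6.3.2.

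**The concern.** The review is triggered by any change, but the protocol's reason for restricting drugs concerns only those that impair healing. Changes to diabetes treatment over 20 weeks are foreseeable: inclusion 1 requires HbA1c above 7.0, and section 1.1 lists uncontrolled diabetes among the obstacles to healing that are treated over weeks to months. Each such change puts the patient's place in the study up for decision, in an open-label trial (5.6).

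Eligibility is a question for entry. Once the graft is on, the patient has been exposed, and ending participation cannot reverse that. Section 7.1.1 keeps the patient in the efficacy population, so the denominator stays while the outcome may be missing. The loss is linked to outcome: a patient already seen healed has a result for complete healing in the first 12 weeks, while one not yet seen healed may have none. A SAP can decide how to count a missing result, but it cannot recover a visit that was never held.

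Adverse-event incidence is also a primary outcome, in a first study in man, and ascertainment relies partly on study visits (6.2.2).

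**Working it through.** **No planned figure to reproduce.** Section 7.2 sets the sample size by precedent, and 7.1.2 limits the analysis to descriptive statistics. The check therefore compares the provisions and then counts what can be lost.

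**Step 1: is removal after a medication change covered by the withdrawal rules?** Sections 4.4 and 6.2.5 make continued eligibility the decision. The four reasons in 4.6.2 and 6.1.3 do not include a medication change. The complications sentence in 4.4 and 6.1.3 protects patients treated for a manageable complication; section 6.2.5 does not repeat it. Other medication changes are not protected.

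**Step 2: what follow-up is owed after removal?** Section 4.6.2 gives one visit, on best effort, with a reference that leads nowhere. Section 6.2.3 adds an HbA1c at the withdrawal visit. Nothing requires the Week 12 or Week 20 visit. Unless the one visit falls at or after Week 12, it does not settle healing status at Week 12. As-required visits (3.1.3, 6.1.3) can narrow the gap between Weeks 4 and 12 for patients in the study, but they are not promised after removal.

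**Step 3: size for the healing proportion.** Enrolment is 15 to 20 (3.1), and the first 1 to 3 patients are left out of the efficacy population (7.1.1). So n runs from 15 − 3 = 12 to 20 − 1 = 19.

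Let x be the number seen healed and m the number of unknown status. Counting all unknowns as unhealed gives x/n; counting all as healed gives (x + m)/n. The width between the two is m/n. The documents give no m, so 1 to 3 is an assumed range:

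| m (assumed) | width at n = 12 | width at n = 19 |
|---|---|---|
| 1 | 1/12 = 8.3 points | 1/19 = 5.3 points |
| 2 | 2/12 = 16.7 points | 2/19 = 10.5 points |
| 3 | 3/12 = 25.0 points | 3/19 = 15.8 points |

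Illustration, assuming half of the observed patients heal:
- n = 12, m = 2, 5 of 10 observed healed: 5/12 = 41.7% to 7/12 = 58.3%.
- n = 19, m = 3, 8 of 16 observed healed: 8/19 = 42.1% to 11/19 = 57.9%.

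If removed patients are still assessed at Week 12, m = 0 and the width is zero.

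**Step 4: scheduled data lost.** There are six follow-up visits (Weeks 1, 2, 3, 4, 12, 20) and three post-baseline SF-12 administrations (Weeks 4, 12, 20).
- Removal between the Week 4 and Week 12 visits drops 2/6 = 33% of visits and 2/3 = 67% of SF-12 administrations.
- Removal between Weeks 12 and 20 drops 1/6 = 17% and 1/3 = 33%.

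One attempted withdrawal visit may replace one of these. Removal after Week 4 leaves the 4-week wound-area outcome untouched.

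**Step 5: adverse events.** Section 9.3.5 requires follow-up of events unresolved at discontinuation. Section 9.3.2 has the investigator notify the sponsor of a reasonably related event that comes to light after discharge, with no duty to look for one after the follow-up period. A new event after removal therefore has no planned visit at which it would be found.

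**The case against.** The strongest reply is that 4.4, read as a whole, supplies the criterion. The review sentence follows the prohibited list and the statement that only drugs harmful to healing are barred, so the clinician is presumably asking whether the new drug is one of those. The review may also simply feed the listed reasons, chiefly the one on new illness. Clinician review of new drugs is ordinary in a first study in man, and exclusion 8 and the 4.4 list can coexist, one for entry and one for the study period. The 5.3 to 8.3 points are just 1/n, the same for any patient lost to any small study.

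Much of this stands. A criterion is implied, and the reach of 6.2.4, headed as medication history, can be argued. A reader might infer that a routine dose change ends participation; no text says so. A reader might also infer that a removed patient is owed no follow-up; 4.6.2 requires the best-effort visit after discontinuation for any reason, and 9.3.2 and 9.3.5 give partial adverse-event follow-up.

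What does not fall is that the decision is worded as one about staying in the study, is triggered by any change, and leads to a follow-up duty that does not secure Week 12. The objection also shows, rightly, that lost follow-up arises under every withdrawal route, and that the four listed reasons are more closely tied to non-healing than a drug change is. The remedy therefore has to reach 4.6.2.

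**Conclusion.** The point holds as a minor to moderate weakness. Followed as written, the protocol can remove a grafted patient after a medication change and leave Week 12 healing unknown if healing has not yet been seen. The cost is 5.3 to 8.3 points of the healing proportion per patient, and new adverse events after removal are captured only passively. This rests on an efficacy n of 12 to 19, on removal before Week 12, and on the one attempted visit not supplying Week 12 status. The number of patients affected is not documented and may be zero.

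A reader might go further and infer that the healing rate will be biased in a known direction. The protocol does not support that: removed patients stay in the efficacy population, and how a missing result is counted is for the SAP. Nor is there any effect on type I error or power, because the study is descriptive. What is at stake is the precision and possible bias of a pilot estimate that 7.1.3.2 says may be used to design later studies.

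**What to change.** - **4.4 and 6.2.5:** state that a medication change is recorded and reviewed by the supervising clinician but does not by itself end participation. Report starting a drug prohibited in 4.4 or named in exclusion 8 as a deviation under 7.1.3.3, with the patient kept in the efficacy population.
- **6.2.4:** limit the eligibility review to medications reported up to Day 0; later drugs are still recorded.
- **4.6.2:** replace the reference to section 6.5.1 with: *any grafted patient whose treatment is stopped or who is discontinued for any reason other than withdrawal of consent will be asked to attend the remaining scheduled visits, at minimum Weeks 12 and 20, for wound, LUMT, SF-12 and AE assessment*. Redirecting the reference to 6.1.3 would not be enough: that section covers Weeks 1 to 20 and does not define the visit owed.

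Clinical decisions about the drug itself and the four withdrawal reasons stay as they are; what changes is that stopping treatment no longer stops observation.

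The cost is a few sentences in an amendment and no visits beyond the existing schedule. The downside is that patients on prohibited drugs, or discontinued for other reasons, stay in the efficacy figures with observed outcomes and may lower them slightly. Attendance can be asked for but not guaranteed, so some results may still be missing.

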4.5 Dietary and Other Restrictions

None. A prudent diet for control of diabetes is encouraged.

4.6 Subject Completion and Withdrawal

4.6.1 Subject Completion

Patients will be required to attend all scheduled appointments specified for the study. If required, appointments may be re-scheduled within a week of the original appointment date. Patients will be required to adhere to home care regimens as provided verbally and in writing by their clinician, including dressing changes, off-loading of the affected limb, and immediate reporting of adverse events such as infection, continued bleeding, excessive inflammation and pain.

4.6.2 Subject Withdrawal

Any subject who voluntarily withdraws (e.g., withdrawal of consent) or is discontinued (e.g., as a result of an AE) from the study prior to the completion of all assessments will be considered as having withdrawn from the study.

Subjects may be withdrawn from the study under any of the following circumstances:

- (i) patient is non-compliant with home care regime (e.g. not wearing off-loading cast),
- (ii) presence of recurrent, untreatable infection,
- (iii) patient develops illness after enrollment that may unduly affect ulcer healing,
- (iv) patient requires more than one re-treatment with DermGEN

When an event such as a family emergency, a transient intercurrent illness (such as a cold) unrelated to study medication, or a remediable act of non-compliance prevents a subject from participating in a scheduled visit but the subject wishes to continue in the study, then with the agreement of the investigator, the clinical staff may attempt to reschedule the visit and retain the subject in the study.

If a subject is prematurely discontinued from participation in the study for any reason after treatment has begun, the investigator or designee must make every effort to perform the assessments scheduled for the Follow-Up Visit (section 6.5.1). The reason for withdrawal will be recorded in the CRF and the subject's medical record.

5. INVESTIGATIONAL MATERIAL INFORMATION

5.1 Investigational Material Identification

Donor human skin received from certified tissue banks will have a unique identifier assigned by the tissue bank. After decellularization processing by DeCell Technologies Inc., each piece of decellularized skin will be given a unique product code assigned by DeCell that will allow tracing to donor tissue received from tissue banks.

5.2 Packaging and Labelling

DermGEN will be provided in a hydrated form stored at room temperature. It will be supplied within a sterile, sealed specimen container containing phosphate buffered saline solution containing streptomycin/penicillin.

DermGEN will be labelled with a product code that will identify it with a specific date of manufacture and tissue source. The product name, DeCell Technologies Inc. logo, and date of manufacture will also appear on the label separately as well as the following text: “Store at room temperature. Do not re-sterilize. Do not freeze. Do not re-seal. Not for sale, for sanctioned clinical trial only. Use aseptic technique to open packaging and handle product inside.”

5.3 Handling and Storage

Shipping in the container provided requires no special handling procedures.

As prescribed on the package label, the product should be stored at room temperature. It should not be re-sterilized, re-frozen, or re-sealed. If not used within 4 hours, it should be discarded according to locally-approved procedures. It is not for sale, and is for sanctioned clinical trial use only.

Use aseptic technique to open packaging and handle product inside.

5.3.1 Receipt of Study Product by Clinical Site

Upon receipt by the study site, the clinical site staff will examine the shipment to verify it has been received in acceptable condition.

5.4 Dispensing

The study product will be dispensed and administered according to study specific procedures. Only subjects participating in the study will receive it. Only authorized clinical staff may supply or administer it.

